1.0 BACKGROUND AND RATIONALE

Breast cancer is the leading cause of cancer and the second leading cause of cancer-related death in U.S. women. ^{1,2} Screening mammography is a contested strategy for reducing breast cancer mortality. There are considerable differences across guidelines for age of initiation and frequency of screening among women at average risk for breast cancer. ³⁻⁵ The U.S. Preventive Services Task Force (USPSTF) recommends against routine screening for women aged 40-49 years, and recommends biennial screening for those aged 50-74 years. ⁶ Conversely, the American Cancer Society (ACS) provides a qualified recommendation for the opportunity to initiate annual screening mammography for women aged 40-44 years, strongly recommends annual screening for women aged 45-54 years, and suggests annual or biennial screening for those 55 years and older. ² These conflicting guidelines highlight concerns about the benefits and harms of screening, and may impact women's decision making. ^{2,3,7-10}

Women with an immediate family history or personal history of breast cancer, genetic risk factors, or prior thoracic or chest wall radiation therapy, and those older in age and with certain modifiable risk factors are likely to benefit from screening mammography. 3-5Conversely, women at average risk may be more vulnerable to certain harms (i.e., physical and psychological harm, financial strain, opportunity costs) associated with screening. 11 Physical harm may result from unnecessary follow-up tests (e.g., biopsies) following the detection of false-positive results (detection of a cancer in error) or from unnecessary treatment due to overdiagnosis (detection of cancer through screening that would not have caused symptoms or death). 11 Most estimates of incidence rates for overdiagnosis in screening mammography range from 19%-31%.2,5,12-20 Women may also experience psychological harm, such as stress or anxiety,²¹ and financial strain might stem from unexpected costs of follow-up tests, loss of income, and concerns about future possible costs. 11,22- 24 Finally, women may experience opportunity costs by having to forgo activities (e.g., self-care, leisure, professional) for further testing, treatment, or symptom management. 11 Differing guidelines and tradeoffs between the benefits and harms of screening may affect women's ability to make informed decisions about whether or not to undergo screening, when to initiate screening, and screening frequency. 2,5,25 Women from underserved populations (e.g., racial/ethnic minority, low socioeconomic status [SES]) and those with low health literacy are at greater risk of misunderstanding screening guidelines, 11-14 and are more likely to experience disparities in screening mammography and breast cancer incidence and mortality, 26-34

Little is known about the best ways of communicating information about the benefits and harms of breast cancer screening mammography to racially/ethnically diverse women with varying levels of SES and health literacy. There is an urgent need for formative research to better understand these issues. Findings will inform strategies to support clinicians in communicating and individualizing discussion of the benefits and harms of screening, and will ultimately help enhance women's ability to make informed decisions about screening mammography. This is critical, as informed decision making takes into account empirical evidence and individuals' values and preferences, and is associated with better knowledge about screening guidelines and the benefits,

risks, and limitations of screening, less decisional conflict and anxiety, greater satisfaction with the decision making process or the decision, and active participation in the decision making process. 35,36

The goal of this project is to create decision support tools for Latina, Black, and non-Latina White women under age 50 with varying levels of health literacy who are considering breast cancer screening mammography.

2.0 OBJECTIVES

To evaluate the potential for implementing the developed decision support tools with Latina, Black, and non-Latina White women in order to collect feasibility data, including acceptability, usability, and limited-efficacy, to prepare for a larger randomized controlled trial.

3.0 PATIENT SELECTION

3.1 Inclusion Criteria

- 1. Latina, Black, or non-Latina White woman
- 2. Age between 40 and 49 years old (inclusive)
- 3. Able to write, read, and understand English

3.2 Exclusion Criteria

- 1. Greater than average self-reported risk of breast cancer, defined as any of the following:
 - a. Self-reported personal history of breast cancer (invasive, ductal carcinoma in situ [DCIS], or lobular carcinoma in situ [LCIS])
 - b. Self-reported personal history of atypical hyperplasia
 - c. Self-reported first degree family member with history of breast cancer (parent, sibling)
 - d. Self-reported known underlying genetic mutation (such as BRCA1/BRCA2 gene)
 - e. Self-reported prior thoracic or chest wall radiation therapy

3.3 Inclusion of Women and Minorities

Latina, Black, or non-Latina White women are eligible for this trial. Women of other races are not eligible.

4.0 REGISTRATION PROCEDURES

This study will register summary accrual statistics to the Siteman Cancer Center OnCore Database. On a quarterly basis, accrual should be grouped according to the demographic data collected. Demographic information includes gender, age, ethnicity, and race. If any piece of demographic information was not collected for those categories, choose unknown.

- 1. In OnCore, navigate to the PC Console for this study and enter the dates of the quarter for which you are entering accrual statistics. (These dates must be inclusive of the same year, e.g. 1/1/2020 3/31/2020, not 12/31/2019 3/31/2020.)
- 2. Then, enter the accrual number for any subjects who are in the same demographic groups of race, ethnicity, gender, and age group. For example, if you have accrued two white non-Hispanic males in their 50s, you will enter that demographic as an accrual group of 2. If you have also accrued an Asian female in her 40s, you will enter her as a separate accrual group (you would enter "1" for the accrual number).
- 3. In addition, you will enter "Research Center" in the drop-down field for "Internal Accruing Reporting Group" and "No disease" in the drop-down field for "Disease Site."

Complete instructions can be accessed in the OnCore Users' Manual: https://cbmiapps.wustl.edu/confluence/display/OSS/6.+Summary+Accruals

5.0 STUDY PLAN

5.1 Study Design

To conduct a preliminary evaluation of the decision support tool, up to 36 women will be recruited to review the decision tool and complete questionnaires to assess informed choice, decisional conflict and confidence, and acceptability. To inform the feasibility testing, 36 women will be randomized to test randomization, measures, and recruitment.

Following this preliminary evaluation of the decision tool and feasibility testing, 198 participants will be randomized on a 1:1 basis to review the decision support tool or control condition of standard breast cancer screening education. Black, Latina, and Non-Latina White participants will be assigned to either the control or intervention condition using 4 and 2 varying block size. They will complete the pre-questionnaire, review the decision support tool/control condition, and complete the post-questionnaire.

5.2 Study Procedures

5.2.1 Recruitment and Consent

Qualtrics Online Research Panels will be used to recruit participants. Qualtrics utilizes samples from traditional, actively managed, double-opt-in market research panels. For hard-to-reach groups, Qualtrics utilizes niche panels brought about through specialized recruitment campaigns. Qualtrics leverages their partner networks to gain access to many hard-to-reach groups. Qualtrics' sample partners randomly select respondents for surveys where respondents are likely to qualify. All strategic sample partners use deduplication technology to provide the most reliable results and retain the integrity of the survey data.

Written informed consent is not required; participants will receive an information sheet, and continued participation (completion of questionnaires, review of materials) will be construed as consent.

5.2.2 Randomization

The sample will be stratified by racial/ethnic subgroups (Black, Non-White Latina, White) for randomization purposes. Participants in these subgroups will be randomized to either the intervention or control arm on a 1:1 basis using 4 and 2 varying block size. The Washington University School of Medicine research team will create the randomization table. Qualtrics will program the randomization table into the survey.

5.2.3 Participation

Measures will elicit participants' perceptions of the tool (Appendix A)/control condition (Appendix B). These measures assess acceptability and informed choice using knowledge, attitudes, intentions, priorities, and values.

Pre-tool/control condition questionnaires are:

- Sociodemographic characteristics (Appendix J)
- Knowledge of Screening Mammography Guidelines and Perceived Benefits and Harms of Screening Mammography (Appendix D)
- Decision Conflict Scale (which collects feelings of being fully informed and clear about the importance of the components for making informed decisions) (Appendix E)
- Decision Self-Efficacy (Appendix F)

Post-tool/control condition questionnaires are:

- Acceptability (Appendix G)
- Preparation for Decision Making Scale (Appendix H)
- Decision Conflict Scale
- Decision Self-Efficacy
- Knowledge of Screening Mammography Guidelines and Perceived Benefits and Harms of Screening Mammography
- Health literacy and health numeracy (Appendix I)

5.2.4 Data Scrubbing

After data collection, records will be removed from the final data set if they meet any of the following criteria as determined by members of the research team. Members of the research team will keep track of how many records were removed and for what reason(s).

Criteria for removal from the final data set:

- The participants do not meet all of the inclusion criteria; or
- The time to complete the questionnaire is less than half of the median time to complete the questionnaire across the full data set; or
- Participants do not respond to, provide nonsensical or incomprehensible answers to, or give responses in a language other than English to at least

four of the eight following knowledge questions:

- o 2.12 Tell me in your own words, what is a mammogram?
- 2.24. What is meant by the term "overdetection" (also called "overdiagnosis")? Please answer in English. If you are not sure, just guess.
- o 2.26. What are some of the benefits of breast cancer screening mammograms? Please answer in English.
- o 2.27. What are the risks or downsides of breast cancer screening mammograms? Please answer in English.
- o 3.49. Tell me in your own words, what is a breast cancer screening mammogram? Please answer in English
- 3.61. What is meant by the term "overdetection" (also called "overdiagnosis")? Please answer in English. If you are not sure, just guess.
- o 3.63. What are some of the benefits of breast cancer screening mammograms? Please answer in English.
- o 3.64. What are the risks or downsides of breast cancer screening mammograms? Please answer in English.

If a participant completes the questionnaire in less than half the median time, it is reasonable to believe that they were unable to process the decision aid(s) in sufficient detail to provide accurate responses to the questions.

Failing to adequately complete the knowledge questions (4 of which are pretool/control and 4 post-tool/control) limit the research team's ability to accurately analyze the feasibility, acceptability, usability, and limited-efficacy of the tool/control.

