6.0 STATISTICAL CONSIDERATIONS

Stratification will be based on racial/ethnic groups (e.g., Latina, Black, non-Latina White). For adequate power, 66 participants from each racial/ethnic group will be enrolled and randomized (198 total).

For knowledge, previous research shows that mean knowledge score is 57 out of 100.³⁶ Compared to usual care, decision aids increased knowledge 13 points (mean difference 13.34 out of 100; 95% CI [11.17,15.51]).³⁶ For decisional conflict scale (0-100), those using a decision aid were more informed by 7 points (mean difference: -7.26 of 100; 95% CI [-9.73, -4.78]), and were more clear

about their personal values by 6 points (mean difference: -6.09; 95% CI [-8.50, -3.67]). ³⁶ Finally, fewer were passive in decision-making (risk ratio 0.66; 95% CI [0.53 to 0.81]). ³⁶ Using a one-sided Mann-Whitney Test, a sample size of 33 provides 80% power at the 0.05 significance level (alpha) to detect a mean knowledge difference of 13 with an estimated standard deviation (SD) of 20, and to detect a mean decision conflict score difference of 6.5 with an estimated SD of 10. Additionally, using a Mantel-Haenszel test, a sample size of 33 provides 80% power at the 0.05 significance level (alpha) to detect a risk ratio of 1.66 assuming the proportion of the informed values-based choice of 0.45 and 0.75 in the control and intervention groups, respectively. Subsequently, to detect the differences between groups with 80% power and 5% Type I error, 33 participants in each control and intervention group will yield a statistically significant preliminary effect. We are making multiple comparisons and recognize that the overall Type I error rate in this study will be greater than 5%. However, this study will allow us to collect adequate data, for planning future large scale studies.

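### Section 5.2.4 lets the team remove randomized records on a subjective reading of free-text answers, half given after exposure, with no stated masking to arm

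*Combined protocol and SAP*

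**What the plan says.** Section 5.2.4 (Data Scrubbing) sets three grounds for deleting a record from the final data set after collection ends, "as determined by members of the research team". Two are mechanical: failing the inclusion criteria, and finishing in under half the median time. The third is that at least four of eight listed knowledge questions are unanswered, answered unintelligibly, or answered in another language. These questions ask the woman to describe a mammogram, overdetection, benefits and downsides in her own words. Four come before the tool or control material and four after it. The team keeps a tally of removals and reasons; the section does not say that the tally is split by arm.

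Section 5.2.2 has participants "randomized to either the intervention or control arm on a 1:1 basis using 4 and 2 varying block size". The research team writes the allocation table and Qualtrics programs it into the survey.

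Section 6.0 powers the knowledge comparison: "Using a one-sided Mann-Whitney Test", 33 per arm is sized "to detect a mean knowledge difference of 13 with an estimated standard deviation (SD) of 20".

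The plan does not mention masking of whoever reads the free text, a second reader, or an analysis that keeps the removed records. Appendix C places the questionnaires and measures in a separate document.

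**The concern.** Deciding that an answer is unintelligible is a human judgement. Here it is made after randomization, partly on answers that follow exposure, and its result is that a randomized participant leaves the analysis. If the reader can see or infer the arm, borderline records can be kept in one arm and dropped in the other. The arms being compared are then no longer the arms that were randomized. Every between-arm comparison is affected, because the whole record goes.

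Knowledge is the most exposed of the powered outcomes. Women who write poor answers to knowledge questions are likely to be those with low knowledge, so uneven removal would move the knowledge mean directly. Section 6.0 says that the data will be used to plan larger studies, so a distorted difference could carry into a later sample size.

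**Working it through.** **1. The plan's own figure.** Inputs from Section 6.0: difference 13, SD 20, one-sided alpha 0.05, power 80%.

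- n per arm = 2 × [SD × (z₀.₉₅ + z₀.₈₀) / difference]² = 2 × [20 × (1.645 + 0.842) / 13]² = 29.3, so 30.
- Dividing by the Mann-Whitney efficiency for normal data: 29.3 / 0.955 = 30.6, so 31.
- Power at 33 per arm is 82.5% by formula with that efficiency, and 81.8% by simulated Mann-Whitney.

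The stated 33 is reproduced on the one-sided basis. A two-sided test would need 38 (39 with the efficiency factor). The sample size is not in dispute here.

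**2. What the removal rule can act on.** Four failed answers out of eight trigger removal. A woman whose four pre-exposure answers are all adequate is removed only if all four later answers fail. If k earlier answers fail (k = 1 to 3), 4 − k failures among the later four are enough. With k = 4 she is removed on baseline answers alone. Answers given after exposure therefore decide the outcome for everyone except that last group. Even baseline answers can be read leniently or strictly by someone who knows the arm.

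**3. Size if removal depends on arm (assumed, extreme case).** Suppose the lowest-scoring share q of one arm is removed and nobody from the other. For normal scores that arm's mean rises by SD × φ(z_q) / (1 − q).

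- q = 0.03: 20 × 0.0680 / 0.97 = 1.4
- q = 0.05: 20 × 0.1031 / 0.95 = 2.2
- q = 0.10: 20 × 0.1755 / 0.90 = 3.9

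The standard error of a difference at 33 per arm is 20 × √(2/33) = 4.92. With a shift b, the one-sided error is 1 − Φ(1.645 − b/4.92) if the tool arm loses the records and there is no true effect. Power for a true 13 is Φ((13 − b)/4.92 − 1.645) if the control arm loses them. Both use the plain normal approximation, with n and SD held at 33 and 20.

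| Share removed, one arm only | Women out of 33 | Shift b | One-sided error (tool arm loses them) | Power for 13 (control arm loses them) |
|---|---|---|---|---|
| none | 0 | 0 | 5.0% | 84.0% |
| 3% | 1.0 | 1.4 | 8.7% | 76.1% |
| 5% | 1.7 | 2.2 | 11.5% | 70.8% |
| 10% | 3.3 | 3.9 | 19.7% | 58.1% |

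The same rule can therefore inflate or hide an effect.

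**4. Scoring, as a conditional illustration only.** Suppose free text carried 20% to 50% of the 0–100 score and coders were 5 to 10 percentage points more generous to one arm. The bias would be 0.20 × 0.05 × 100 = 1 point to 0.50 × 0.10 × 100 = 5 points. By the same error formula, a bias favouring the tool gives about 7.5% to 26.5% at 33 per arm. At 99 per arm (198/2) the standard error is 20 × √(2/99) = 2.84, and the range is about 10% to 54.5%. Simulated Mann-Whitney tests give 7.5% to 24.6% and 10.1% to 52.3%. Neither the weight nor the generosity comes from the documents, and the weight could be zero.

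**The case against.** The strongest reply is that the documents describe removal only. A reader might infer that unmasked coders hand-score the free text and so tilt the knowledge outcome toward the tool. The documents do not support that reading:

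- The quoted phrase governs which records are deleted. No section says that free text is scored by hand, who would score it, or whether it counts toward the 0–100 score. A scoring key could be in the separate measures document.
- The plan is silent on masking, which is different from saying that readers know the arm. Writing the allocation table does not put each woman's arm before the reader, and the export that readers receive is not described.
- The removal test is about intelligibility. It gives no credit for correctness, and its direction depends on which arm loses more low scorers.
- Knowledge is one of three powered outcomes. None is named as primary, and the stated aim is feasibility with limited efficacy.
- A pooled 99 v 99 comparison is not what the power statement describes.

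All of this stands, and it confines the scoring figures to illustration. It does not answer the narrower point. The removal rule is written down, it rests on judgement, it uses answers given after randomization, and nothing in the plan prevents the arm from being known when it is applied. The rationale in Section 5.2.4 ties these answers to the limited-efficacy analysis, so some use of them as outcome data is plausible, though its form is unknown.

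**Conclusion.** The concern holds for record removal. As written, Section 5.2.4 permits arm-dependent exclusion after randomization, and this could bias the between-arm comparisons in either direction. Under the extreme assumption that one arm alone loses its lowest scorers, one to three women out of 33 shift the knowledge mean by 1.4 to 3.9 points, about 11% to 30% of the planned 13 (1.4/13 and 3.9/13). Real removals would be less selective and would probably occur in both arms, so these figures are nearer an upper bound for those numbers of removals than a forecast. Bias in scoring, and the error rates in step 4, apply only if free text counts toward the score and the coders know the arm; the documents establish neither. The gap is worth closing before data cleaning begins. The planned 33 per arm is unaffected.

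**What to change.** In Section 5.2.4, state that:

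1. the free-text answers are exported without the allocation field and in random order;
2. team members decide adequacy and removal from that export;
3. those decisions are locked before allocation is merged back;
4. removals are reported by arm and by reason;
5. if any free-text item counts toward the knowledge score, it is scored from the same arm-masked export.

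Masking the time point is secondary for a between-arm comparison and can be optional. The differing wording of the first pre and post items may reveal it anyway.

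The cost is a small amount of data handling, with no extra staff or participants. Two limits remain. Masking may be imperfect where an answer echoes the tool's own vocabulary. Masking also cannot remove a real effect of the material on how women answer. The count of removals by arm would show an imbalance from either source.

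### Section 5.2.4 removes randomised women partly on post-exposure information, and no between-arm analysis that keeps them is planned

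*Combined protocol and SAP*

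**What the plan says.** Section 5.2.4 (Data Scrubbing) removes records once data collection is over, on any of three grounds. The first, failing the inclusion criteria, is a baseline matter and is not at issue. The other two are:

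- **Time rule.** A record goes if "The time to complete the questionnaire is less than half of the median time to complete the questionnaire across the full data set". The cut-off is one value pooled over both arms. The reason given is that, for such women, "it is reasonable to believe that they were unable to process the decision aid(s) in sufficient detail".
- **Answer rule.** A record goes if the participant "do not respond to, provide nonsensical or incomprehensible answers to, or give responses in a language other than English" on at least four of eight open knowledge items, "4 of which are pretool/control and 4 post-tool/control".

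Members of the research team decide, and they record the number removed and the reasons. The section mentions neither arm nor masking.

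Section 5.2.3 lists knowledge among the measures repeated after the tool or control. Section 2.0 gives the aim as feasibility data, including acceptability, "usability, and limited-efficacy, to prepare for a larger randomized controlled trial". Section 6.0 powers one-sided between-arm tests at 33 per arm, within 66 women randomised per racial/ethnic group. It names no analysis that keeps the removed women.

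**The concern.** Randomisation protects the comparison of women as assigned. Here the analysed set is chosen afterwards, partly from what happened after exposure.

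- **Time rule.** The arms read different material: the tool in Appendix A and an NCI web page (Appendix B). If the clock includes reading, and one text takes longer, a single pooled cut-off removes more women from the quicker arm.
- **Answer rule.** A woman who fails only the four post-exposure items is removed, and her answers there may depend on what she read. Deciding that an answer is nonsensical takes judgement, so unmasked judging is a second route to imbalance.

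At stake is the limited-efficacy estimate that is meant to inform the larger trial. As written, the plan offers no second between-arm comparison that would show whether a difference came from the tool or from the removals.

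**Working it through.** **1. The plan's own figure.** For knowledge (difference 13, SD 20, one-sided 0.05, 80% power), n = 2 × [20 × (1.645 + 0.842) / 13]² = 29.3. Dividing by the Mann-Whitney efficiency 3/π gives 30.6, so 31 per arm. Simulated power at 33 per arm is 0.82. For proportions 0.45 and 0.75, n = 32. The stated 33 is reproduced, with every randomised woman analysed.

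**2. Time rule: inputs.** Only the half-median cut-off and SD 20 come from the documents. The rest is assumed: log-normal total times with log-SD σ = 0.5, no true effect, and time-knowledge correlation ρ from 0.1 to 0.5. If reading is a share w of the shorter arm's time and the reading-time ratio is r, the total-time ratio is R = (1 − w) + w·r. With w = 0.25, r = 1.5 gives R = 1.125 and r = 2 gives R = 1.25.

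**3. Time rule: formulas.** Share removed = Φ[(−ln 2 ± ½ ln R)/σ], with plus for the faster arm. Spurious difference = 20·ρ·[h(p_fast) − h(p_slow)], where h(p) = φ(z_p)/(1 − p).

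Example for R = 1.25: Φ(−1.163) = 12.2% and Φ(−1.609) = 5.4%, about 4 and 2 of 33 women. Then h = 0.231 and 0.116, and at ρ = 0.5 the difference is 20 × 0.5 × 0.1156 = 1.16 points.

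| R | Removed, faster / slower arm | Spurious points at ρ = 0.1 / 0.3 / 0.5 |
|---|---|---|
| 1.125 | 10.2% / 6.6% | 0.12 / 0.37 / 0.61 |
| 1.25 | 12.2% / 5.4% | 0.23 / 0.69 / 1.16 |
| 1.5 (upper case) | 16.3% / 3.7% | 0.42 / 1.27 / 2.12 |

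With σ from 0.4 to 0.7 and R from 1.125 to 1.25, the range is again about 0.1 to 1.2 points. The standard error of the knowledge difference is 20·√(2/33) = 4.9 points at 33 per arm and 20·√(2/99) = 2.8 pooled.

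**4. Error rate.** These are simulated one-sided Mann-Whitney tests at 0.05 after scrubbing, with the tool arm the faster one.

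- R = 1.125 to 1.25: about 0.05 to 0.08 at 33 per arm, and up to about 0.10 at 99 per arm.
- R = 1.5: up to about 0.11 and 0.17 respectively.
- Control arm faster, 33 per arm, R = 1.125 to 1.25: the rate falls to between 0.05 and 0.03.
- All women kept: about 0.05 throughout.

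**5. Answer rule.** The same formula with illustrative splits gives 0.1 to 0.7 points for 12% vs 8% removed, and 0.3 to 1.7 for 15% vs 5%.

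**6. Equal counts are not enough.** With 10% removed from each arm, h(0.10) = 0.195. If removal correlates 0.1 with knowledge in one arm and 0.5 in the other, the difference is 20 × (0.5 − 0.1) × 0.195 = 1.6 points.

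**The case against.** The strongest reply is that this is a feasibility study on an online panel, where screening out careless respondents is sensible, and that the possible shift is at most 1.2/13 = 9% of the planned effect on the central inputs. That stands, and it limits the weight of the point. It does not remove it, because limited efficacy is a stated objective and Section 6.0 plans significance tests. That section's remark that overall Type I error will exceed 5% concerns multiple comparisons, not selection after randomisation.

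The time mechanism is also conditional. It needs a clock that includes reading, materials that take different times, and time related to knowledge. Section 5.2.4 does not define the clock, although its rationale suggests that reading counts. If reading is excluded, the reading-time mechanism disappears, but the clock still covers the post-questionnaire. The time rule is numeric and set in advance, so masking matters mainly for the answer rule.

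The answer rule is milder than it may look. It removes absent, unintelligible or non-English answers, not wrong ones, and removal on post-exposure items alone requires failing all four. Part of it is therefore missing outcome data under another name.

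A reader might go further and infer that scrubbing invalidates the comparison or favours the tool. The documents do not support that: they give no timings, text lengths or removal rates, and the bias could run either way. Nor do they support the opposite inference, that similar removal counts in the two arms would settle the matter (step 6).

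**Conclusion.** The point holds as a modest weakness in the analysis plan that is cheap to repair. Two removal rules use post-exposure information at least in part, and the plan provides no between-arm comparison without them. The direction of any bias is unknown. Its size rests entirely on the assumed times and correlations above: small beside 13 points and below one standard error, with an error rate that matters more if strata are pooled.

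With no true effect, the bias is zero only if equal shares of the same kind of women are removed from both arms, or if removal is unrelated to outcome. With a true effect, even equal removal changes the women to whom the estimate applies.

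**What to change.** In Sections 5.2.4 and 6.0:

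- Add one between-arm analysis of all eligible randomised women with post-questionnaire data, by assigned arm and without the time or answer-quality removals. Present it beside the scrubbed analysis; the team can choose which is main.
- In that analysis, score blank or nonsensical knowledge answers by one rule that is the same in both arms, for example as not correct.
- Have existing staff who are blind to arm judge the open-text answers.
- Report removals and missing outcomes by arm and by reason. This is needed because the added set is itself limited to women with post-questionnaire data.
- Report both estimates and discuss any difference. Significance in both need not be required, since that would cost 2 to 11 points of power against the scrubbed test alone.

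The cost is rewording two sections and one extra analysis of data already collected. The downside is that inattentive respondents may dilute the added estimate. If the women kept gain nothing, 13 points becomes 13 × (1 − 0.083) = 11.9 when about 8% are kept, or 13 × (1 − 0.18) = 10.7 when 18% are. Simulated power at 33 per arm is then about 76% in the added analysis against 79% scrubbed, or 66% against 74%. If they gain like the others, the added analysis has the higher power: 82% against 79%, or 81% against 74%. These shares are assumptions too.
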